#### **Primary Outcome Measures:**

- Total number of patients enrolled -> KPI: minimum 50 patients enrolled;
- Total number of active patients -> KPI: minimum 40 active patients;
- Total number of patients who drop off, meaning that started the study and had less than 4 active weeks
- Average number of active weeks for each patient: the average number of active weeks is evaluated as the total number of active weeks divided by the number of patients enrolled -> KPI: 8 weeks (excluding drop off before 4 weeks)
- Activity participation, measured in average minutes per day dedicated to exercises with WeReha (measured during active weeks only) -> KPI: min. 45'/week
- Acceptance of the rehabilitation platform WeReha by the patient, evaluated through a questionnaire completed at the end of the study by every participant who consents to the study (see attachment ... )
- Previous results will be analysed on different age/gender groups. Age groups are: <55, 55-70, 70-85 both for male and female, for a total of six groups. Target would be to enroll patients within these groups as homogeneously as possible, but since we cannot foresee patients distribution there are no KPIs set for this outcome

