## Study goals and objectives

The goal of this study is to assess the acceptance and validity of a new technology such as WeReha for home rehabilitation of patients following a stroke episode either in sub-acute or chronic phase. The investigation will be conducted in two different countries: two sites in Northern Ireland and one in Italy.

This study is part of the EU funded Magic PCP project [5], where three different companies will perform similar types of study. Every company will be assigned from September 2018 a trust in Northern Ireland and a site in Italy from among the following: Hospital Le Torrette, Ancona, University D'Annunzio, Chieti, ASL3 Pinerolo, Torino. Once a company has received approval for funds to perform the study (before September 2018), it will also be assigned the site in Italy and then it will apply for the Ethical Committee of that site. Every company is also required by the Magic PCP project [5] to provide 75 devices per country (150 in total). From now on, we will refer to the number of patients relevant to the Northern Irish site..

Let us define the terms and list assumptions we will use throughout the protocol:

- “enrolled patient”: a patient is considered enrolled in the study if they are within the inclusion criteria and voluntarily accept to participate and sign the consent form
- “active week”: a week in which the patient has performed at least three sessions with WeReha for a minimum of 15 minutes each (as measured by the software)
- “active patient”: a patient that has used the device for at least 4 “active weeks”
- “maximum time frame of usage”: 20 weeks, according to patients and clinicians feedback collected during our feasibility study (see [Safety Consideration](#) section)
- “end of usage”: if the participant does not have four active weeks in the first eight weeks of usage or the patient has reached the “maximum time frame of usage” or the patient has voluntarily decided to interrupt the study (drop-off)

The study aims to evaluate as a primary outcome quantifiable measure, the acceptance of technology, through analysis of the following:

- number of enrolled patients at the end of the trial period will be evaluated in order to understand the degree of acceptance of a technology such as WeReha, with the minimum target of 50 patients.
- number of “active weeks” with the device among the patients enrolled

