- ii)     ii) how to position the sensor inside it,
- iii)     iii) how to move the object in order to reach the game’s target.

Once the sensor is worn or positioned inside an object, before starting the game, the patient is guided through a calibration phase to measure the sensors initial orientation in the space which acts as a reference position for all the movements recorded during the game. This process not only makes the measures more accurate but also nullifies any sensor wrongly positioned when worn (i.e. sensor overturning, rotations, inclinations respect to the body frontal plane).

In this pilot study investigators will recruit as many patients as possible as defined within the inclusion and exclusion criteria. There will be 75 devices available at the site from September 2018 to December 2019. Each patient will be provided with a WeReha device including the tablet and its charger, the inertial sensor and its charging station and cable, a kit of elastic straps together with a Velcro pocket and the 3 plastic objects. Every device can be used twice in order to assess as many patients as possible, providing a new set of straps and smart objects (that are to be considered single user only) and cleaning the other components by following specific and simple instructions provided by CoRehab.

Participants will be consented following a diagnosis of stroke and will keep the device for a maximum of 20 weeks following discharge from the hospital setting. This amount of time has been decided following review by clinicians and therapists during our earlier feasibility work. After that the tablet and the sensor will be collected, cleaned to ensure no cross contamination and meeting infection control guidelines within each Trust and made available for further use... The elastic straps with the pockets and the smart objects are the only personal and single use components, which will be disposed of after use... Secondary outcomes will only be assessed on “active patients”.

There will be a WeReha server available as a cloud solution, compliant with NCSC Cloud Security Principles, on which the web application will run and all the data will be collected whenever a patient’s device is connected to the internet. It is important to highlight that internet connection is not mandatory for the device to work properly as it will propose exercises to the patient as they were prepared initially after patient’s discharge. Then, whenever the device is

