tutorials and instructions of exercises, software navigation and interaction, understanding of games, ease-of-use to handle the “smart objects”, effectiveness of feedback provided during game, patients attitude with respect to exercises to be performed by themselves or with the aid of a support. Only at the end of the last session patients were asked if they appreciated this innovative and technological home rehabilitation solution and how long they would have used the device willingly.

Furthermore in order to receive as much feedback as possible from the clinical point of view, WeReha was also evaluated by a professionals group (2 physiotherapists, 1 psychiatrist and 1 psychologist) of another private clinic, Fondazione Santa Lucia in Rome, where the staff have a great experience in stroke patients rehabilitation with technology. We asked them to test the device on their own (not on patients) and to answer the same questionnaire underwent to Franca Martini’s patients from a clinical point of view.

After the two month study period all the answers from the two sites and the comments from Villa Martini’s patients were collected and evaluated. Particularly, WeReha has been evaluated to be a simple and easy-to-use device for stroke patients, even for those who do not have much experience with technological devices (pc, tablet, smartphone...). The first day of training on the usage of the device seemed to be sufficient to guarantee an independent use by patients, especially with regards to the software navigation. It has also been described as motivational and fun by patients, so much so that they would continue the training with WeReha at home on average three months without finding it boring and repetitive. Most importantly, the indication to use the device for 3 months was also provided by clinical staff supervising the feasibility study in both sites, and this is the reason why we have set the maximum time frame to 12 weeks.

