## Duration of the study and patient's timeline

The total duration of the study is expected to be approximately 1 year and 4 months, starting at the beginning of September 2018 and ending at the end of December 2019.

Each patient will be required to keep the device for 20 weeks following discharge after which they will return the WeReha device to the hospital. In cases where a participant uses the device for

four of the first eight weeks the device has been assigned, the patient's generated output will be considered as valid.

When a patient starts the evaluation period, some clinical measures will be taken, as well as when (s) he returns the device. Such clinical evaluations are specified in the 'Methodology' section.

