## Anticipated Results of the Study

As stated, this trial is part of the Magic-PCP project [5], and the results of the study aim to demonstrate the impact of the usage of technology for stroke patients and community on a large scale. The project anticipates that devices will be accepted by patients and integrated in their home treatment routine, that they will use it regularly and with the expectation that it improves motivation and as a consequence their quality of life and motor functions.

Results will be collated by the buyers group also with other ongoing studies within the umbrella of the Magic PCP project and compared eventually with existing studies that we referred to.

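### Apart from an eight-week rule, the usage KPIs ignore when active weeks fall and how long the device was held, so meeting them does not show regular use

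*Combined protocol and SAP*

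**What the plan says.** The definitions are in Study goals and objectives. An active week is "a week in which the patient has performed at least three sessions with WeReha for a minimum of 15 minutes each". An active patient is "a patient that has used the device for at least 4 “active weeks". Primary Outcome Measures then sets the targets:

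- at least 50 patients enrolled and at least 40 active;
- for average active weeks, "KPI: 8 weeks (excluding drop off before 4 weeks", although the same bullet defines the average with all enrolled patients in the denominator;
- 45 minutes a week of exercise, "measured during active weeks only".

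Drop-off is counted there as fewer than four active weeks and has no target.

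Data Management and Statistical Analysis rules out a statistical analysis of the primary outcomes and judges them good if the KPIs are reached. It also names the time that patients use the device at home as something the study aims to evaluate. Anticipated Results of the Study expects devices to be "integrated in their home treatment routine, that they will use it regularly".

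One rule concerns timing. A patient without four active weeks in the first eight reaches end of usage (Study goals and objectives) and is reviewed by the PI, who expects to take the device back but may let the patient continue (Methodology). Four of the first eight weeks also makes the patient's output valid (Duration of the study and patient's timeline). No later usage check is stated.

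The loan period is not consistent. Study Design says that patients "will keep the device for a maximum of 20 weeks following discharge from the hospital setting", and Duration of the study says "Each patient will be required to keep the device for 20 weeks following discharge". The Project summary and Safety Considerations give 12 weeks.

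**The concern.** The KPIs alone decide whether the primary outcome is called good, so what they can distinguish matters. They are totals of active weeks, and minutes within those weeks. Early use followed by abandonment and use that continues to the end of the loan can give identical values. A patient who stops for good after four active weeks is not even a drop-off as Primary Outcome Measures defines it.

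For a home device, the difference between initial interest and lasting adoption is central to acceptance. The feasibility volunteers said that "they would continue the training with WeReha at home on average three months without finding it boring and repetitive", so a decline within a longer loan is at least plausible on the plan's own evidence. A good verdict could be read as evidence of sustained use when the measures behind it do not address that question.

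**Working it through.** **Inputs.** Active week: at least 3 sessions of at least 15 minutes. Active patient: at least 4 active weeks. Targets: 50 enrolled, 40 active, mean of 8 active weeks, 45 minutes a week (the outcome is described per day, but the target is taken as written, per week). Early rule: 4 active weeks within weeks 1–8. Loan: 20 weeks, with 12 as the alternative. The targets are fixed numbers without a derivation, so there is no plan calculation to reproduce. The check is whether the definitions allow the targets to be met without later use.

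**Minutes target.** The minimum in any active week is 3 × 15 = 45 minutes. Since only active weeks are counted, the average cannot fall below 45. The target is met by definition.

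**Mean active weeks.** Mean = total active weeks / number of patients, under both readings of the denominator. Each case has 50 enrolled and a 20-week loan; patients not listed as active contribute no active weeks.

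| Case | Active patients | Mean, drop-offs excluded | Mean, all enrolled | Later use |
|---|---|---|---|---|
| A: 40 patients active in weeks 1–8 only | 40 | 320/40 = 8.0 | 320/50 = 6.4 | none in weeks 9–20 |
| B: 40 patients active in weeks 1–10 only | 40 | 400/40 = 10.0 | 400/50 = 8.0 | none in weeks 11–20 |
| C: all 50 active in weeks 1–8 only | 50 | 400/50 = 8.0 | 400/50 = 8.0 | none in weeks 9–20 |
| D: 40 patients active in weeks 1, 3, 5, 7, 10, 13, 16, 20 | 40 | 320/40 = 8.0 | 320/50 = 6.4 | all 40 active in week 20 |

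Every active patient in all four cases satisfies the eight-week rule. With drop-offs excluded, A meets every target. With all enrolled in the denominator, A misses the mean; even if the ten drop-offs had three active weeks each, it would be (320 + 30)/50 = 7.0. B and C meet every target on either reading.

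**What the KPIs cannot separate.** A and D have the same KPI values. By four-week block, the share of active weeks among the 40 active patients is 100%, 100%, 0%, 0%, 0% in A and 50%, 50%, 25%, 50%, 25% in D.

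**Scale.** Eight active weeks is 8/20 = 40% of a 20-week loan and 8/12 = 67% of a 12-week loan. The active-patient threshold is 4/20 = 20% or 4/12 = 33%.

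**The case against.** The strongest reply is that this is a pilot of acceptability with descriptive targets, and a cumulative-use target is a legitimate choice. That stands as a defence of reporting the total. It does not turn the total into evidence of regular use, which the protocol anticipates.

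Other parts of the reply also stand and limit the point:

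- A reader might infer that timing is ignored altogether. It is not: the eight-week rule ties four active weeks to weeks 1–8. But it tests early use only, and abandonment afterwards passes it.
- A reader might infer that regular use cannot be shown at all. Annex A provides for a record of each daily session, exported for outcome measurement, and an observed mean near 20 would itself show sustained use. The limitation lies in the KPIs and in the absence of a planned analysis over time, not in the data.
- A reader might infer that stopping at about week 8 is to be expected. The feasibility work does not support that. It records stated willingness from 20 volunteers after four weekly sessions at a rehabilitation centre, and three months lies beyond week 8.
- A reader might take regular use over 20 weeks as the protocol's stated aim. The anticipated-results sentence gives no period, and the loan length is itself inconsistent.

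The questionnaire at device return asks about intention to keep using the device (Annex B, items 19–22), but it has no target and does not measure observed use.

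**Conclusion.** The point holds in this limited form. With drop-offs excluded from the mean, all KPIs can be met with no use in the last 12 of 20 weeks (60% of the loan). With all enrolled in the denominator and 40 of 50 active, they can be met with no use in the last 10 of 20 weeks (50%). On a 12-week loan the corresponding gaps are 4/12 = 33% and 2/12 = 17%. The 45-minute target carries no information on either reading.

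Meeting the KPIs therefore does not show regular use, although the logged sessions could. The cases are constructed to show what the definitions permit and are not forecasts. They assume that patients excluded as drop-offs leave both numerator and denominator, and that the minutes target is per week. The trial is not invalidated: this is a gap between the measures and one of the plan's stated expectations, and it should be closed before the results are analysed.

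**What to change.** First reconcile the 12-week period (Project summary, Safety Considerations) with the 20-week period (Study goals and objectives, Study Design, Duration of the study, Follow-Up), and settle one denominator for the mean. Then, from the session logs already planned:

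1. Report the percentage of patients given the device who are active in each week from home set-up to the end of the planned loan. Count early voluntary return, or removal for non-use, as not active. Treat patients whose loan is cut short by study closure as not observed from that point. With closure at the end of December 2019, this affects home starts after about 13 August 2019 for 20 weeks, or about 8 October 2019 for 12 weeks.
2. Measure minutes per week over all weeks of the planned loan, with inactive weeks at their actual minutes or zero, instead of in active weeks only.
3. Base any statement about regular use on item 1 in the later part of the loan, not on the 8-week total alone.

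Active weeks divided by weeks held should not be the main measure. It gives 8/8 = 100% to a patient who returns the device after eight active weeks and 8/20 = 40% to one whose eight active weeks span a 20-week loan, so it scores early return as full use.

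The cost is small. No new visits or devices are needed, but home set-up and return dates must be linked to the logs, since the anonymised export described in Annex A lists neither. Inpatient use must be kept out of the count, as Methodology already provides. The reported usage figures will probably look less favourable.

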## Project summary

WeReha is an innovative device for the home rehabilitation of stroke patients developed within the scope of the EU funded project MAGIC-PCP [5]. WeReha is a system that allows patients to perform exercises in a home environment with remote supervision integrated within regular rehabilitation. The principle on which the product is based is that of biofeedback guided rehabilitation, designed to stimulate muscle recovery and contribute to a more effective and more motivating rehabilitation of neuro-motor patterns. WeReha is completely adaptable, allowing only authorized to assign exercises, by planning specific sequences of movements.

WeReha product is composed by the following elements:

- a tablet with a proprietary application on it (the “WeReha app”)
- an inertial sensor with accelerometers, gyroscopes and magnetometers (the “sensor”)
- elastic straps allowing the user to wear it on different parts of the body (the “straps”)
- a series of 3D printed objects where the sensor can be placed that become animated (the “smart objects”)
- a web portal for clinical staff through which they can manage and monitor users (the “web-application”)

The WeReha app presents the patient with a series of rehabilitation exercises in the form of a number of interactive games, driven by body movement, which is captured by the sensor or the hand specific movements using the smart objects. A session with WeReha always starts with a questionnaire on the system, through which the software gains an understanding of the patient's health conditions and the presence or not of a caregiver for the session. Based on this questionnaire, the software adapts the daily session to minimise risks while maintaining a high level of rehabilitation to help the patient reach their goals. The device works with and without an internet connection, but when the device is connected to the internet, supervisors are able to provide supervision and remote support through a web application.

The web application is hosted on a dedicated server located inside the hospital. Only trained staff will be provided with access to the web application with a unique username and password required for sign on. The exercises assigned for the client to perform at home, are at the discretion of the clinician who is caring for the patient and might require the presence of a caregiver.

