## Study Design

This is a pilot study to investigate acceptability of usage of technology to aid rehabilitation of post stroke patients at home. An innovative inertial sensor and interactive games based device, called WeReha, has been designed and developed to best meet the rehabilitation needs of stroke survivors... WeReha is composed of:

- i) an Android tablet running dedicated software
- ii) an inertial blue-tooth sensor with 3D accelerometer, 3D gyroscope and 3D magnetometer
- iii) a kit of elastic straps with a Velcro pocket to wear the sensor on specific body segments (chest, thigh, foot and wrist)
- iv) a kit of 3D printed plastic objects (a hourglass, a plate and a joystick) that become "smart" positioning tools through the use of sensors embedded inside them)

The WeReha software will present the patient with a series of rehabilitation exercises in the form of interactive games, using the worn sensor or the "smart objects". All the games in WeReha are based on the tracking the three dimensional movements of body segments or the smart objects through the sensor applied to them. The exercises integrated in WeReha have been designed with physiotherapists and clinicians, and are akin to traditional rehabilitation following a stroke that can involve any of the lower limbs (hip, knee and ankle) the upper limb (shoulder, elbow and wrist), the head and the trunk. Some require a sitting position, others a standing position with or without a support, according to the ability of the patient and whether there is supervision or not.

During an exercise which requires the worn sensor, a specific elastic straps among those of the kit has to be used. Dependent on the specific exercise sequence that will be performed; at startup the patient will be guided by the software step by step to:

- i) position the elastic strap around a specific body segment;
- ii) position the sensor inside the pocket;

- iii)     iii) Attach the pocket to the elastic strap. Particularly, the body segments involved in wearing the straps are the trunk, the thigh, the foot and the wrist, for balance, lower limb, foot-ankle and upper limbs exercises respectively.

A similar tutorial guides the patient on how to make the objects “smart” and thus trackable in the space and on how to use them correctly during games that simulate aspects of the real life. Specifically, the instructions provided include

- i)     what object to be used for the specific exercise;

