## Data Management and Statistical Analysis

As the primary outcomes of the study are designed to evaluate the impact and acceptance of a new rehabilitative technology for stroke patients, a statistical analysis on the primary outcomes will not be conducted. On the other hand, the study clearly aims to evaluate the number of patients, meeting the inclusion/exclusion criteria that are willing to use this technology and the time they will be using the devices at home. It has also to be noted that this study is part of a research project (Magic-PCP, [5]) where 3 companies will provide their solutions to 1 hospital in Italy and sites in NI, i.e. each company will run a similar trial with identical numbers on different sites. The request and the funding to provide 75 devices on each country and aim at performing a validation on maximum 2 patients per device is a clear requirement of the project. We have then defined the primary and secondary outcomes that we consider crucial for evaluating our proposed technology.

The primary outcome will be evaluated in an anonymised form and considered good if planned KPIs are met or exceeded. Secondary outcomes will be evaluated using an unpaired test to compare pre and post intervention measured values, whereas the Chi-square test will be used to detect the significance of outlier proportions, p values smaller than 0.05 will be considered statistically significant. All calculations will be performed using the Matlab software tool (The Mathworks Inc., Natick, MA, USA). We are also interested in evaluating possible correlations among results for the different groups of patients under examination (male and female <55 years old, 55-70, more than 70) to be better prepared for a future clinical investigation of our device.

All details related to the Data Management are provided in Annex A - Technical Data Management of the present document.

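### The 45-minutes-a-week activity KPI equals the entry condition for an active week, so on a single count of minutes it cannot be missed; which minutes count, and the day/week unit, are left open

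*Combined protocol and SAP*

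**What the plan says.** Study goals and objectives defines an active week as "a week in which the patient has performed at least three sessions with WeReha for a minimum of 15 minutes each", timed by the software.

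Primary Outcome Measures lists "Activity participation, measured in average minutes per day dedicated to exercises with WeReha", and the same line continues "measured during active weeks only) -> KPI: min. 45'/week". The list of primary measures in Study goals and objectives also gives this quantity as average minutes per day.

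Data Management and Statistical Analysis plans no statistical analysis of the primary outcomes. They are to be "considered good if planned KPIs are met or exceeded". The other primary KPIs are 50 patients enrolled, 40 active patients, and an average number of active weeks with "KPI: 8 weeks (excluding drop off before 4 weeks" as its target.

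Three passages describe what a session contains besides exercise:

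- Project summary: "A session with WeReha always starts with a questionnaire on the system".
- Study Design, on positioning the strap and sensor: "at startup the patient will be guided by the software step by step to".
- Study Design, once the sensor is in place: "before starting the game, the patient is guided through a calibration phase".

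**The concern.** A success threshold is informative only if the data could fall on either side of it. Here the average is restricted to weeks that have already passed a 45-minute filter, and is then compared with 45 minutes. A patient who does the bare minimum to make a week count also meets the participation target in that week.

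The KPIs are the only yardstick for the primary outcomes. A target met by construction would be reported as a target achieved, and a reader could take it as evidence that patients accepted the device.

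The ways in which the KPI could be missed depend on two definitions that the plan does not give: which minutes count, and whether the target is weekly or daily. If these are settled after the usage data are seen, the reading can be chosen to suit the result.

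**Working it through.** **Inputs.** Sessions per active week: at least 3. Minutes per session: at least 15. KPI: 45 minutes per week, active weeks only. The first two come from the definitions in Study goals and objectives, the third from Primary Outcome Measures.

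**Step 1: one count, weekly unit.** The minimum for an active week is 3 × 15 = 45 minutes, exactly the KPI. Longer or additional sessions only add to it. An average of values that are each at least 45 is at least 45, whether taken over pooled weeks or over patient means. The KPI is therefore met whenever at least one active week exists. Patients with no active week contribute nothing to the average. Entering them as zero could bring it below 45, but the restriction to active weeks does not read that way.

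**Step 2: two counts, weekly unit.** Suppose d minutes of each session are not exercise. The documents give no durations, so d = 1 to 10 is an assumption to show the range.

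- Minimum exercise time in an active week is 3 × (15 − d): 3 × 14 = 42 minutes at d = 1, and 3 × 5 = 15 minutes at d = 10.
- With three sessions a week, the KPI is missed only if the mean session is shorter than 45/3 + d, that is 16 minutes at d = 1 and 25 minutes at d = 10.
- Three 30-minute sessions with d = 10 still give 3 × 20 = 60 minutes.

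On this reading the KPI can fail, but only for sessions close to the minimum length.

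**Step 3: the unit.** The weekly figure corresponds to 45/7 = 6.4 minutes per calendar day, or 45/3 = 15 minutes per session day. If 45 minutes per day were meant, the weekly total depends on the denominator:

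- calendar days: 45 × 7 = 315 minutes, or 315/3 = 105 minutes per session at three sessions;
- three session days: 45 × 3 = 135 minutes, or 45 minutes per session.

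Take three 30-minute sessions a week. Safety Considerations gives 30 minutes as the minimum session length in the feasibility work, although those sessions were held once a week in a clinic. The total is 90 minutes. That is 90/45 = 2.0 times the weekly target, but 90/315 = 29% or 90/135 = 67% of the daily one. The same usage passes on the weekly reading and fails on either daily reading.

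**The case against.** The strongest reply is that a redundant KPI changes no overall verdict. If all KPIs must be met, one that always passes cannot create a false success, and the enrolment, active-patient and active-weeks targets still bind. The study is a pilot without inference on its primary outcomes, and mean minutes in active weeks is a legitimate measure of intensity, separate from persistence. All of this stands. It limits the weight of the point, but it does not make the threshold informative.

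Second, the unit may be less open than it looks. The KPI is written per week, and 45 is exactly 3 × 15, which suggests that weekly was meant. A reader might infer from the per-day wording that the real target is 45 minutes a day and that patients would fall far short. The documents do not support that. They support only that measure and KPI are in different units with no conversion.

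Third, the source of the minutes is settled. The software times the sessions, and Study Design has primary-outcome data collected automatically on the device. What remains open is whether session time equals exercise time. The overhead may be small: Methodology says sessions are arranged to keep sensor changes to a minimum. Safety Considerations reports tutorials found too long by 11 of 20 volunteers, but also that the instructions and tutorial language were then revised.

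A reader might also infer that limiting the average to active weeks conceals low use overall, and try to compute an all-weeks average from the KPIs. The documents do not support such a figure. It would require zero minutes in every non-active week, yet a week with two 20-minute sessions is non-active and still holds 40 minutes. Persistence is already covered by the active-patient, drop-off and active-weeks outcomes.

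**Conclusion.** The point holds, conditionally. On the written weekly unit, and with session and exercise minutes as one count, the lowest possible result is 45 minutes a week, equal to the KPI. Meeting it is then not evidence of acceptance. With two counts, the minimum falls to between 42 and 15 minutes under an assumed 1 to 10 minutes of overhead per session. The KPI can then fail, but only for short sessions. The documents do not say which case applies, and the measure and its target are in different units.

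It would go too far to say that the trial is bound to be declared a success, or that the KPI can never be missed. The other three KPIs can fail, and the guarantee depends on a single count of minutes and at least one active week. The defect is a decision rule with one uninformative, loosely defined component. It is worth correcting because the plan judges its primary outcomes by nothing else.

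**What to change.** Before results are seen:

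1. State the measure and its KPI in one unit. If a daily unit is kept, say whether the denominator is calendar days or days of use. State whether questionnaire, set-up, tutorial and calibration time counts, and use the same count in the active-week definition and in the minutes measure.
2. If the threshold then still equals the entry condition, as it will with a common count and the weekly unit, report mean minutes in active weeks as a description of intensity. Do not count 45 minutes a week as a success criterion under Data Management and Statistical Analysis.

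The cost is rewording one primary outcome and one definition, plus a sponsor decision on unit and count. The downside is that one primary outcome loses its pass/fail target. Two consequences need checking. The documents do not show that exercise time is logged apart from session time; if it is not, the common count can only be session time. If the common count excludes overhead, fewer weeks may qualify as active, which carries through to the active-patient, drop-off and active-weeks outcomes.

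A figure for minutes over all weeks could be added as description, but it is optional and not needed to repair this defect.
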